### 7.3 Data Analysis

#### Bioinformatic analyses

Bioinformatic analyses of the various *omics* datasets will be conducted in collaboration with Fondazione Istituto Italiano di Tecnologia (CMP3VdA, Genoa and Aosta).

##### - DNA analysis using Illumina technology

For genomics, DNA variants identified will be analyzed jointly by CMP3VdA and the clinical units in Genoa and Milan. The analytical pipeline will generate the following files:

1. **FASTQ** – containing raw sequencing reads and per-base quality scores; the starting point of bioinformatic analyses.
2. **BAM** – containing mapped reads aligned to the human reference genome.
3. **VCF/BCF** – containing identified variants for each individual.

Pipeline steps:

- a) Quality assessment, filtering, and trimming of raw reads.
- b) Read alignment to the reference genome.
- c) Identification of SNVs, indels, structural variations (SVs), rearrangements, and copy number variations (CNVs).
- d) Generation of a comprehensive variant database.
- e) Compilation of control population variants and allele frequency tables.
- f) Comparison of patient-specific variants and allele frequencies with control populations and public cohorts.
- g) Prediction of variant effects and association with genomic features.
- h) Prioritization of patient-specific variants and their association with neurodegenerative disorders, leading to genomic-based stratification.

The pipeline employs standard tools, notably **GATK (Genome Analysis ToolKit)** from the Broad Institute, widely considered the gold standard for variant analysis. As certain GATK tools are computationally intensive, IIT uses NVIDIA GPUs and **Clara™ Parabricks** software for accelerated processing, achieving a 15–20× reduction in runtime for mapping and variant calling.

##### - Variant annotation

VCFs will be annotated using tools such as **SnpEff**, leveraging multiple public databases that catalog variant effects, including:

- ALZFORUM (AD mutations): <https://www.alzforum.org/>
- PPMI (PD mutations): <https://www.ppmi-info.org/>
- Alzheimer's Disease Neuroimaging Initiative (ADNI): <http://adni.loni.usc.edu/about/>
- Gene4PD <http://genemed.tech/gene4pd/>

- Parkinson's Disease DNA Variant Browser: <https://pdgenetics.shinyapps.io/variantBrowser/>
- ClinVar (variant–phenotype relationships)
- Databases containing allele frequencies of known variants gnomAD, 1000 Genomes, dbSNP
- ALSoD (ALS mutations): <https://alsod.ac.uk/>

Variants will be classified according to **SIGU** and **ACMG international guidelines**.

#### - Structural variant analysis

Given the high false-positive rate of short-read SV detection, a consensus approach integrating multiple tools (Manta, Lumpy, CNVnator, BreakDancer) will be applied. Variants will then undergo consensus filtering with **SURVIVOR**, re-genotyping with **Smoove**, and false-positive reduction with **Duphold**, maintaining >99% true positives while removing ~61% false positives. Additionally, **MELT** will be used for transposable element insertions. SV frequency will be estimated using an in-house algorithm, and annotations added with **AnnotSV** and **SVAFotate**. CNVs will also be evaluated using **CNVkit**.

All results will populate a central database for variant prioritization, disease association, and data mining.

#### - Reproducibility and updates

All analyses will be performed within standardized virtual environments (containers) ensuring reproducibility across samples. Updates to software and databases (e.g., genome builds, annotation tools) will be periodically implemented, reprocessing prior datasets to maintain comparability. Variant annotation will be continuously updated as novel pathogenic variants emerge in the scientific literature.

In summary, the pipelines employed for genomic data analysis utilize a sequence of widely adopted software tools for variant identification (including PARABRICKS, with BWA and GATK adapted for GPU usage, and ANNOVAR and SnpEff for annotation) applied to both coding genes and non-coding regions of the genome. Typically, the most recent human reference genome is used, currently version Hg38. Several databases containing known variants are employed to filter out neutral variants and to identify those associated with the disease of interest. In particular, gnomAD and the 1000 Genomes Project (Table 1) are used, as they are representative of the global population in terms of both neutral and deleterious mutations. This strategy allows us to exclude variants currently lacking functional impact and to identify those likely responsible for disease.

It is important to note that, regardless of the software employed, variant definition and classification are carried out according to internationally recognized standards such as ACMG guidelines.

This approach ensures that all samples are analyzed using the same software and database versions stored within the container (Table 2). As soon as new software updates become available, the virtual machine will be updated accordingly, and all previously processed samples will be reanalyzed. This guarantees reproducibility across different samples. Furthermore, the variant annotation software will be updated frequently, as mutations currently of unknown significance may, in the future, be classified as pathogenic owing to continuous advances in scientific research.

Software or Database	Version
Clara™ Parabrick	4.1.0
SnpEFF	5.0e
ANNOVAR	20221123
Cosmic	v94
GnomAD	v3.1.2
dbSNP	155
PolyPhen	v2
Sift	6 Dec 2019
CADD	v1.6
FATHMM	v2.3
Genoma	Hg38
ADNI	NA
PPMI	NA
ALZFORUM	NA
Gene4PD	NA
Parkinsons's Disease Variant Browser	0.2.1
ClinVar	NA
1000 Genomes Project	NA
MELT	2.2.2
ALSoD	NA
BreakDancer	1.4.5
Manta	1.6.0
CNVKit	0.9.9
Lumpy	0.2.13

CNVnator	0.3.3
Smoove	0.2.6
SVAFotate	0.0.1
AnnotSV	3.2.3

**Table 2.** List of software and databases employed, with the corresponding version currently in use, where available. NA, Not Applicable.

### DNA Analysis with Nanopore Technology

Depending on research outcomes and project requirements, a subset of cases within this study may be sequenced using third-generation Oxford Nanopore Technologies (ONT). This approach may be particularly useful for improved characterization of structural variants, methylation profiling, validation purposes, and other specific analyses.

ONT provides a suite of analysis tools. For DNA sequencing, ONT currently recommends the Guppy basecaller, which is the most performant for initial basecalling. For alignment of sequencing reads to the reference genome, Lra will be employed, while SNV calling will be performed using Clair3.

For structural variant detection, alignment will be performed with Lra, and variant calling with CuteSV.

ONT technology also enables haplotype phasing, allowing determination of the allele on which a variant is located. This will be performed using the WhatsHap tool.

### Base Quality Estimation of Sequenced Reads

In sequencing-by-synthesis (SBS) technology (Illumina), the quality of each base in a read is quantified by assigning a Phred Quality Score (PQS), computed by a dedicated algorithm. This score represents the probability that a base has been miscalled. A PQS of 10 corresponds to an expected error rate of 1 in 10 bases (90% accuracy), a PQS of 20 to 1 in 100 (99% accuracy), and a PQS of 30 to 1 in 1000 (99.9% accuracy). When sequencing quality reaches Q30—the benchmark for next-generation sequencing (NGS)—virtually all reads are expected to be error-free and unambiguous.

### RNA Analysis

RNA sequencing (RNA-Seq) data, generated using commercially available platforms and those installed at CMP3VdA laboratories (currently Illumina and/or ONT), may be used to investigate gene expression and potential correlations between non-coding variants and expression changes. Expression quantitative trait loci (eQTLs) highlight variants that, although not altering protein structure, may affect transcriptional regulation and gene function. Additional analyses of transcript modifications, such as RNA methylation, may also be performed.

Gene expression analyses will be carried out using the DESeq2 package in R^81.

RNA sequencing with ONT technology further enables characterization of transcript isoforms generated by alternative splicing, in addition to quantifying expression. For instance, in Alzheimer's disease, certain TAU isoforms resulting from alternative splicing have been associated with increased disease risk.

### Epigenomic Analysis

For the study of molecular modifications regulating gene expression—such as DNA methylation, one of the most common epigenetic modifications—state-of-the-art technologies available both commercially and at CMP3VdA will be employed. Both Illumina and ONT sequencing platforms can be applied for this purpose. In particular, the PromethION 24 platform directly extracts methylation information during DNA sequencing, thereby enabling simultaneous characterization of both the genetic and epigenetic landscape in a single sequencing run. Identification of disease-specific methylation signatures (episignatures) will be performed using the most up-to-date bioinformatic tools available in the scientific community for this class of analyses.

## Pathway Analysis

For unresolved cases where the diagnostic solution is not readily identifiable, secondary analyses will be conducted. Variants, including common ones with potential functional effects, will be aggregated and investigated at the pathway level. Specifically, the involvement of patient-specific gene pathways will be compared with the individual's clinical status.

Causative variant identification will be supported by annotation tools such as ANNOVAR and SnpEff, which classify variants as loss-of-function (LoF) or missense. Genes implicated will then be analyzed using available platforms such as STRING and GeneMANIA to assess associations between pathways, gene lists, and variant frequencies.

Gene network and pathway enrichment analyses will be performed to identify biological processes linked to the studied disorders. Commonly used bioinformatic tools such as Gene Set Enrichment Analysis (GSEA) and g:Profiler will be applied for this purpose.

## Blood Biomarkers of Neurodegenerative Diseases

Several blood biomarkers currently available and associated with cognitive impairment and other neurodegenerative disorders will be analyzed. These include amyloid-beta 1-42 (A $\beta$ 1-42), amyloid-beta 1-40 (A $\beta$ 1-40), tau protein phosphorylated at threonine 181 (pTau181), and neurofilament light chain (NFL), a sensitive indicator of neuroaxonal damage in various degenerative conditions. These molecules are key elements in the identification and understanding of pathological mechanisms specifically associated with Alzheimer's disease (A $\beta$ 1-42, A $\beta$ 1-40, pTau181) and, more broadly, with neurodegenerative diseases (NFL). They also provide information regarding disease progression and patient staging. Quantification of these biomarkers will be performed using a chemiluminescent enzyme immunoassay (CLEIA) on the Lumipulse G600 II platform (Fujirebio, Ghent, Belgium). Additional biomarkers, once validated and available, will also be analyzed.

## Experimental Validation of Data

From a bioinformatics perspective, NGS-based sequencing methods—particularly Illumina short-read platforms—present a very low error rate ( $\sim 10^{-5}$ ). However, results obtained through sequencing technologies may be validated using Sanger sequencing, which has a per-base accuracy of 99.999%, and/or other conventional approaches, thereby reducing the likelihood of error to a negligible level.

## 7.4 Statistical Analysis

### Sample Size

Given the nature of this study, sample size is not determined by a formal statistical power calculation but rather by projections of i) the number of patients with neurodegenerative diseases expected to be referred to the two experimental centers during the 10-year project period, and ii) an estimated compliance rate of approximately 80%.

We anticipate enrolling at least 1,000 patients with neurodegenerative diseases, distributed approximately as follows:

- a) Parkinson's disease (PD): ~30% of cases
- b) Parkinsonism: ~5% of cases
- c) Dementias:
  - Alzheimer's disease (AD): ~30% of cases
  - Frontotemporal dementia (FTD): ~10% of cases
  - Young Onset Dementia (YOD): ~5% of cases
  - Mild Cognitive Impairment (MCI): ~5% of cases
- d) Amyotrophic lateral sclerosis (ALS): ~15% of cases.

Additionally, ~200 geriatric controls with negative neurological evaluation and negative family history of neurodegeneration will be enrolled as internal controls.

The projected cohort of ~1,000 patients is based on the epidemiology of neurodegenerative diseases observed at IRCCS Policlinico San Martino (Genoa) and Fondazione IRCCS Policlinico Ca' Granda (Milan). The expected distribution across disease categories should allow reliable characterization of clinical and molecular subgroups.

### Variant Analysis and Validation

In genomic studies, initial evaluation focuses on determining whether identified variants are:

- i) previously established as causative of neurodegenerative disease,
- ii) novel variants potentially acting as disease-driving mutations, or
- iii) benign polymorphisms catalogued as non-pathogenic.

Variant assessment will rely on open-access reference databases widely used as benchmarks in clinical and population genomics. To validate associations between identified variants and neurodegenerative diseases, analyses will include:

a) **Control genomes:** Databases such as the 1000 Genomes Project, the International Parkinson's Disease Genomics Consortium (IPDGC), and PPMI will be used to determine the minor allele frequency (MAF) of each variant in European and Italian populations, with a particular focus on the 107 Tuscan genomes sequenced for the 1000 Genomes Project. Considering the prevalence of rare variants in neurodegenerative diseases and the MAF of common variants linked to late-onset AD and PD, the cut-off for rare variants will be set at 0.01. This analysis will allow prioritization of variants absent from control databases.

b) **Disease-specific databases:** Variants will also be analyzed against disease-focused resources such as ALZFORUM, ADNI, PPMI, and Project MinE, which contain genomic data from thousands of patients with AD, PD, and ALS. This will support validation of both individual variant–disease associations and combinations of rare variants enriched in patient genomes. Custom databases will be built from ADNI, PPMI, and MinE to provide allele frequencies and enable systematic comparison between enrolled individuals and these large patient cohorts.

Rare variants will be further assessed for potential disease susceptibility effects in the presence of other variants within the same genome. To this end, the number of variants per sample will be analyzed in both patient and control populations. Odds ratios (ORs) with corresponding 95% confidence intervals (95% CIs) will be calculated. Q-value correction (an extension of the False Discovery Rate) will be applied, and receiver operating characteristic (ROC) curves will be computed to assess test accuracy.

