### 3. STUDY DESIGN

**NeurOmics** is a multicenter, prospective, observational study enrolling patients diagnosed with neurodegenerative diseases, including Parkinson’s disease and degenerative parkinsonisms, neurodegenerative cognitive disorders at the stage of mild cognitive impairment (MCI) or early/late-onset dementia, and motor neuron diseases (ALS). The study aims to identify pathogenic genomic variants and/or dysregulated molecular pathways in these patients by performing whole-genome sequencing and integrating these data with transcriptomic, epigenomic, and/or proteomic profiles. It further aims to identify novel biomarkers for the diagnosis and monitoring of neurodegenerative diseases through the analysis of biological samples (e.g., blood and derivatives), including liquid biopsy approaches using the most advanced technologies currently available.

The study plans to enroll at least **1,000 individuals** with neurodegenerative disease (see section *7.4 Statistical Analysis*).

Thanks to the availability of large public databases containing whole-genome sequences from healthy populations, such as **gnomAD** and the **1000 Genomes Project**, these datasets can be used as controls for variant identification in participants diagnosed with PD and parkinsonisms, early- and late-onset dementias (including MCI), and ALS. For example, the 1000 Genomes Project provides a catalog of common human genetic variants derived from self-reported healthy individuals, which has become a widely used reference in biomedical genomics.

To confirm the association of variants identified in this study with the relevant neurodegenerative disease, their presence will be checked against curated mutation repositories, including **ALZFORUM** and the **Alzheimer’s Disease Neuroimaging Initiative (ADNI)** (<http://adni.loni.usc.edu/>) for AD, and **PPMI** for PD. For subjects with MCI, genomic data deposited in ADNI (including controls, AD cases, and MCI) will be used. For ALS, the study will leverage the **Project MinE** database and genomic resources.

The case series and available data from each reference database are summarized in **Table 1**, while detailed statistical methodology is provided in section *7.4 Statistical Analysis*.

Database Name	Type of Sequencing	Number of Genomes (WGS), Exomes (WES), Genes, SNPs, Indels, SVs or CNV	Number of Subjects	Type of Case

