### Statistical Approaches

Descriptive statistics will be generated to report the percentage of variants relative to the total enrolled cohort and to the control populations (European and Italian), stratified by disease (PD, parkinsonism, AD, FTD, YOD, ALS, and MCI), individual genes, and specific mutations.

Molecular–genetic data (single variants or variant groups) and clinicopathological data (diagnosis, disease stage, prognostic/predictive parameters, survival) will be analyzed using both numerical and graphical approaches. Frequency and contingency tables will be constructed, and statistical indices (means, percentiles, standard deviation) will be computed. Data will be visualized through histograms, boxplots, and scatterplots. Appropriate statistical tests—including t-tests, Fisher's exact test, and others depending on the formulated hypotheses—will be applied. Enrolled patients will be monitored through active follow-up as part of routine diagnostic care. Data regarding disability progression, disease course, and overall survival will be analyzed by diagnosis, mutation, or mutation combinations, as well as treatment received, using Kaplan–Meier survival analysis.

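### The per-sample variant count comparison names only public databases as control genomes and plans no common calling, so data source may be confounded with case status

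*Protocol*

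**What the plan says.** Section 7.4, Variant Analysis and Validation, first describes the reference data. Under its control-genomes item: "Databases such as the 1000 Genomes Project, the International Parkinson's Disease Genomics Consortium (IPDGC), and PPMI will be used" to obtain allele frequencies in European and Italian populations, with emphasis on 107 Tuscan genomes. It then turns to the joint effect of rare variants within a genome: "the number of variants per sample will be analyzed in both patient and control populations". The effect measure is fixed: "Odds ratios (ORs) with corresponding 95% confidence intervals (95% CIs) will be calculated". On multiplicity, the same paragraph adds: "Q-value correction (an extension of the False Discovery Rate) will be applied". ROC curves are planned as well.

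Other sections bear on who the controls are:

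- Section 3 says of gnomAD and 1000 Genomes that "these datasets can be used as controls for variant identification in participants". Table 1 labels both as controls. It lists 1000 Genomes as 3,202 genomes at 30x including 602 trios, and PPMI as mixed whole-genome and whole-exome data.
- Statistical Approaches refers to "control populations (European and Italian").
- Sample Size adds about 200 "geriatric controls with negative neurological evaluation and negative family history of neurodegeneration will be enrolled as internal controls". They are not mentioned again.

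On processing, section 7.2 sets a minimum in-house depth of 30X. Section 7.3 calls study samples with Parabricks/GATK and a consensus filter for structural variants. It keeps software versions identical by running samples in one container and reanalysing earlier ones after each update. It does not say that public genomes go through that container.

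**The concern.** A count of variants per person depends on how variants are called as well as on biology: caller, filters, callable regions and assay all move it. If patients are counted from in-house calls and controls from published call sets, every such difference lines up with case status. The test then picks up technical differences together with any disease burden. Enrolling more patients does not help; it makes a spurious difference easier to detect. False discovery control does not help either, because it limits chance findings and not a systematic shift.

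The bias can run either way. Extra calls in patients would look like burden. A stricter in-house filter would hide a real burden or create an apparent deficit. What is at stake is the inferential part of the first primary objective, the search for new susceptibility variants.

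**Working it through.** The protocol gives no alpha, power or calling-error figure for this comparison, so there is no stated figure to reproduce.

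**Inputs from the protocol.** 300 cases (about 30% of 1,000, as for PD or AD); 1,000 cases in all; 107 Tuscan genomes; 3,202 samples in 1000 Genomes; about 200 internal controls.

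**Assumptions not in the protocol.** No true difference; mean count m = 10 per sample, Poisson; relative calling shift d = 0.5%, 2% or 5%; two-sided 5% z-test on the mean count. This test stands in for the planned odds ratios.

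**Formulas.** SE = √(m(1/n₁ + 1/n₂)); z = d·m/SE; false rejection = Φ(z − 1.96) + Φ(−z − 1.96).

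Example, 300 vs 107, d = 5%: SE = √(10 × (1/300 + 1/107)) = 0.356; z = 0.5/0.356 = 1.40; rejection 29%.

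| Cases vs controls | SE | d = 0.5% | d = 2% | d = 5% |
|---|---|---|---|---|
| 300 vs 107 | 0.356 | 5.2% | 8.7% | 29% |
| 1,000 vs 107 | 0.322 | 5.3% | 9.5% | 34% |
| 300 vs 3,202 | 0.191 | 5.8% | 18% | 74% |

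**Sensitivity to the mean.** For 300 vs 3,202, m = 3 gives 8.8% (d = 2%) and 30% (d = 5%); m = 1 gives 6.3% and 13%. A larger mean raises the rates.

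**A second model.** With normal counts and an assumed between-person coefficient of variation (CV) of 5%, 10% or 20%, SE relative to the mean is CV·√(1/n₁ + 1/n₂). A 1% shift then gives false rejection of 43%, 14% or 7% for 300 vs 107, and 91%, 38% or 13% for 300 vs 3,202. The direction agrees; the size depends on the spread of the count.

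**Structural variants.** Section 7.3 says the in-house filter keeps over 99% of true calls and removes about 61% of false ones. Suppose it is applied to patients only, and a share φ of raw calls is false. The retained count is 0.99(1 − φ) + 0.39φ: 0.96 at φ = 5% and 0.81 at φ = 30% (φ assumed). That is a shift of −4% to −19%, against finding burden.

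**The case against.** A reader might infer that the protocol states that patient counts are compared with public genomes called on other pipelines. It does not. The count sentence names no control source, and the control-genomes item uses the databases for allele frequencies. The internal controls are also a control population. How public genomes will be processed is neither stated nor denied. Compiling control variants is a step of the study's own pipeline in section 7.3, and custom databases are planned. All this stands, so the pipeline difference is an inference. The inference is still the natural one: public databases are the only genomes the protocol calls controls, no re-calling is planned, and nothing says that the internal controls will be sequenced.

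A reader might also infer that depth is the cause. The documents do not support that for 1000 Genomes, which Table 1 lists at 30x, the same as the in-house minimum. The possible differences are calling and filtering and, for PPMI, assay.

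Nor should rates based on all 3,202 genomes be read as expected values. They treat members of 602 trios as independent. They also ignore the protocol's focus on European and Italian controls, although section 7.3 describes this source as representing the global population. The number of European samples is not given, so the relevant control number lies between 107 and 3,202. The mean of 10 and the shifts have no anchor in the protocol.

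Finally, detailed calling rules often belong in a statistical or bioinformatics plan, and their absence is not the point here. The choice of comparator is, because the protocol already names the contrast, its measures and the candidate control genomes.

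**Conclusion.** The point holds in conditional form. As written, the protocol plans an inferential case-control comparison of variant counts, names only public genomes as controls, and provides no common processing for them. If public call sets are used unchanged, data source is confounded with case status, and neither q-values nor a larger sample corrects it.

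Under the Poisson model with a mean of 10, false rejection for 300 cases is about 9% (2% shift) or 29% (5% shift) with the Tuscan genomes, and up to 18% or 74% with all of 1000 Genomes. It is near nominal, 5% to 6%, if the shift is only 0.5%. For 2% shifts it stays at or below 9% if the mean count is 3 or less. The structure of the problem does not depend on these assumptions; its size does.

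**What to change.** In Variant Analysis and Validation, state that per-sample counts, their odds ratios and the ROC curves are tested only against controls processed in the same container as the patients. These can be:

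- the roughly 200 internal controls, with an explicit statement that they are sequenced and run through the container; and/or
- public raw reads re-called in that container and restricted to jointly callable regions.

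Before interpreting any burden result, check that synonymous-variant counts per sample agree between cases and controls. Keep the public databases for allele-frequency filtering and annotation.

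**Cost.** With internal controls alone, the SE for 300 cases is √(10 × (1/300 + 1/200)) = 0.289, about 51% wider than 0.191 with 3,202 public genomes. It is still narrower than the 0.356 with the 107 Tuscan genomes. Re-calling public reads would recover precision at the price of compute. If sequencing of the internal controls is not already planned, about 200 further genomes must be budgeted, so this should be settled before sequencing is scheduled.

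### Variants are selected because patients carry them and then compared with controls, so odds ratios for very rare variants are biased upward under the null

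*Protocol*

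**What the plan says.** The pipeline in Section 7.3 (DNA analysis using Illumina technology) calls variants, tabulates control variants and frequencies at step e, and then at step f plans "Comparison of patient-specific variants and allele frequencies with control populations and public cohorts". Step h prioritises the patient-specific variants and links them to disease.

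Section 7.4 (Variant Analysis and Validation) sets out to validate associations for the variants that have been identified. It puts the rare-variant cut-off at a MAF of 0.01 and says of the comparison with control genomes: "This analysis will allow prioritization of variants absent from control databases". After a sentence about counting variants per sample in both patients and controls, it continues: "Odds ratios (ORs) with corresponding 95% confidence intervals (95% CIs) will be calculated". Q-values and ROC curves follow. Section 7.4 (Statistical Approaches) adds contingency tables and Fisher's exact test for single variants as well as groups of variants, with descriptive results split by disease.

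On the control side, Section 3 says of gnomAD and 1000 Genomes that "these datasets can be used as controls for variant identification in participants diagnosed with PD and parkinsonisms", and Table 1 lists both as controls. Section 7.4 gives 1000 Genomes, IPDGC and PPMI as examples of control sources, points to European and Italian populations, and singles out 107 Tuscan genomes. About "200 geriatric controls with negative neurological evaluation" are to be enrolled as internal controls.

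**The concern.** An odds ratio, its interval and Fisher's test are calibrated for a set of variants fixed without looking at who carries them. Here the same patients supply the variants and then supply the case counts. A neutral variant that happens to appear in one patient enters the set; an equally rare one that happens to appear only in a control need not. Ranking variants by absence from controls selects a second time, on the other cell of the table.

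The consequence is an OR above 1 without any association, largest for private and ultra-rare variants. Those matter here because Primary Objective 1 seeks variants not yet recognised as causes or susceptibility factors, and Secondary Objective 1 carries findings into family counselling.

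**Working it through.** **Inputs.**
- Whole cohort: "We anticipate enrolling at least 1,000 patients with neurodegenerative diseases", so 2,000 alleles (Section 7.4, Sample Size).
- Strata, same section: PD or AD at about 30%, so 300 patients and 600 alleles; "Amyotrophic lateral sclerosis (ALS): ~15% of cases", so 150 patients and 300 alleles; parkinsonism, YOD or MCI at about 5% each, so 50 patients and 100 alleles.
- Controls: gnomAD 76,156 genomes (152,312 alleles) and 1000 Genomes 3,202 (6,404 alleles), Table 1; 107 Tuscan genomes (214 alleles); 200 internal controls (400 alleles).
- Assumptions: one heterozygous carrier, and each database used in full, because the size of an ancestry-matched gnomAD subset is not given.

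There is no planned figure to reproduce: "sample size is not determined by a formal statistical power calculation".

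**1. Inflation from requiring at least one patient copy.** For a neutral variant of frequency q in N patients, the expected patient frequency, given that it was seen, is overstated by 1/(1 − exp(−2Nq)). For N = 300 and q = 0.0001 this is 1/(1 − exp(−0.06)) = 17.

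| Patients | q = 0.0001 | q = 0.001 | q = 0.01 |
|---|---|---|---|
| 1,000 | 5.5 | 1.16 | 1.00 |
| 300 | 17 | 2.2 | 1.00 |
| 150 | 34 | 3.9 | 1.05 |
| 50 | 101 | 10.5 | 1.6 |

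**2. One patient copy against no control copies.** The OR is infinite. The exact lower 95% limit is (0.025/0.975) × (control alleles/case alleles), that is, the allele ratio divided by 39. When control alleles outnumber case alleles, the two-sided Fisher p is case alleles/(case + control alleles). For 300 patients against gnomAD: 152,312/600/39 = 6.51 and 600/152,912 = 0.0039.

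| Patients | Controls | Exact lower limit | Fisher p |
|---|---|---|---|
| 1,000 | gnomAD, all | 1.95 | 0.013 |
| 300 | gnomAD, all | 6.51 | 0.0039 |
| 150 | gnomAD, all | 13.0 | 0.0020 |
| 50 | 1000 Genomes | 1.64 | 0.015 |
| 300 | 1000 Genomes | 0.27 | 0.086 |
| 300 | 200 internal | 0.017 | 1.0 |
| 300 | 107 Tuscan | 0.009 | 1.0 |

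The exact limit passes 1 when control genomes exceed 39 times the number of patients: 39 × 300 = 11,700, 39 × 1,000 = 39,000 and 39 × 50 = 1,950. A Woolf interval with 0.5 added crosses earlier, at about 2,460 genomes for 300 patients and 8,190 for 1,000. By that method 300 patients against 1000 Genomes gives 32 (1.30 to 788).

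**3. Range of frequencies affected.** Neutral variants were simulated with 1,000 patients against gnomAD, keeping those seen in at least one patient and using Woolf intervals (nominal share of lower limits above 1: 2.5%).

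| MAF | Median OR | Lower limit above 1 |
|---|---|---|
| 1e-5 | 76 | 100% |
| 1e-4 | 5.1 | 15% |
| 5e-4 | 1.14 | 5.9% |
| 1e-3 | 1.02 | 4.6% |
| 0.01 | 0.99 | 2.9% |

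**4. Q-values.** The plan gives no level, so 0.05 is assumed, with Benjamini–Hochberg as a stand-in. If only single-copy variants absent from gnomAD are tested in the whole cohort, every p is 0.013, every q is 0.013, and all pass. If all patient-seen variants with MAF below 0.01 are tested, with neutral frequencies distributed as 1/f, none reaches q < 0.05. With 300 patients, private variants pass only if they exceed 0.0039/0.05 = 7.8% of the tested set. Of three simulated frequency spectra (q^-1, q^-1.5, q^-1.8), only the steepest went above that share.

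**The case against.** The strongest reply is that the OR sentence directly follows one about counting variants per sample in patients and in controls, so its nearest reading is a burden OR, which is close to the remedy proposed here. That stands for a burden count built with the same rule on both sides. It does not cover a burden restricted to variants chosen for absence from controls, where the control count is zero by construction. Nor does it cover the single-variant tests under Statistical Approaches or the individual variant–disease associations named in Section 7.4.

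Second, a reader might infer that any private variant will show an interval above 1. The documents do not support that. The gnomAD figures use all its genomes, while Section 7.4 points to European and Italian controls. With 300 patients, the exact interval includes 1 against 1000 Genomes, the Tuscan genomes and the internal controls.

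Third, a reader might infer that control-only variants are never tested, or that the q-value fails in general. Step e does compile control variants, and nothing says they are then dropped. The q-value failure needs a tested set limited to control-absent variants, or an unusually steep frequency spectrum; Section 7.4 prioritises such variants but does not say that q-values run on them alone.

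Fourth, the definition of the tested set, the minimum allele count and the q-value family may sit in an analysis plan that is not shown. Their absence is not the point. The point is the order of steps that the protocol does state.

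**Conclusion.** The concern holds in a bounded form. The stated sequence of finding variants in patients, favouring those absent from controls and then computing ORs and Fisher tests against controls uses the same data to select and to test. For any per-variant OR, or any burden count over variants selected that way, the OR is biased upward under the null for very rare variants. In the whole cohort this matters mainly below a MAF of about 5e-4; in a 50-patient stratum the inflation is still 10.5-fold at 0.001. Intervals that exclude 1 from a single carrier arise against the full gnomAD set in every group, and against 1000 Genomes in the 50-patient strata (exact lower limit 1.6). In larger groups they depend on the interval method and on the size of the matched control set, which the protocol does not give.

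A reader might also infer that Primary Objective 1 will therefore return neutral variants as findings. The protocol does not support that: variants are classified by ACMG and SIGU guidelines, and no passage makes an interval or a q-value the rule for declaring one. This is a correction worth making before analysis; it does not undermine the study.

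**What to change.** In Section 7.4, state three things:
- The per-sample burden OR uses one qualifying rule, based on frequency and annotation, applied identically to patients and controls, and variants seen only in controls count.
- Single-variant tests are run only above a minimum minor allele count in patients and controls combined, and q-values are computed over that full set.
- Private variants are reported descriptively by ACMG class, without OR, CI or q-value.

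In a check with 1,000 patients against gnomAD, drawing neutral variants from patients and controls together lowered the share with Fisher p < 0.05 from 4.8–5.2% to 2.4–2.6%.

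The cost is a change of wording and a little more analysis work, with no new data. The sponsor gives up ORs for single-carrier variants.
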